13.	Provisions for AE and Device Defect Reporting.....	43
13.1.	AE	43
13.1.1.	Definition of AE.....	43
13.1.2.	Determination of AE Severity.....	43
13.1.3.	Recording of AE.....	43
13.2.	Device Defect	43
13.3.	SAE	44

13.4. Reporting Procedures and Contact Information	44
14. Deviation from Clinical Trial Protocol and Regulations for Protocol Amendment	45
15. Direct Access to the Source Data and Documents	46
16. Finance and Insurance	46
17. Contents to be Covered in Clinical Trial Report.....	46
18. Confidentiality Principle	47
19. Agreement on Publication of Trial Results	47
20. Responsibilities Assumed by All Parties.....	48
20.1. Responsibilities of the Sponsor:	48
20.2. Responsibilities of Study Site and Investigator:.....	48
References	50
Investigator's Statement	51
Appendix 1 List of Study Sites and Investigators	52
Appendix 2 ASPECTS Scale	53
Appendix 3 mTICI Image Grading Criteria:.....	54
Appendix 4 mRS:	55
Appendix 5 NIHSS:.....	56

Protocol Abstract

Protocol title	Study on Effectiveness and Safety of Ghunter Revascularization Device for Endovascular Treatment of Acute Ischemic Stroke (A Prospective, Multicenter, Randomized Controlled, Non-inferiority Study)
Protocol version No. and date	V3.0/February 9, 2022
Sponsor	Sinomed Neurovita Technology Inc.
Device name	Ghunter Revascularization Device
Device classification	Class III medical device
Study objective	To verify the effectiveness and safety of Ghunter Revascularization Device for endovascular treatment of acute ischemic stroke
Sample size	220 subjects
Number of study sites	No less than 10 sites, competitive enrollment
Indications for use	Ghunter Revascularization Device is indicated for use in ischemic stroke patients whose symptom onset are within 24 h.
Control setting	Test group: Sinomed Neurovita Ghunter Revascularization Device Control group: Solitaire FR
General inclusion criteria	
 1) ≥ 18 years old; 2) NIHSS ≥ 6 at randomization; 3) Pre-onset mRS < 2; 4) Acute ischemic stroke was diagnosed; 5) Within 24h from the stroke onset to the completion of femoral artery puncture (regardless of whether intravenous thrombolysis has been performed); the time point of stroke onset is defined as the time point at which the patient is last known to be normal; 6) The subject (or his/her guardian) agrees to participate in this study and signs the informed consent form (ICF).
Angiographic inclusion criteria	
 1) Cerebral CT or MR should be performed when the time from the stroke onset to the completion of femoral artery puncture of a patient is ≤ 6h; 2) Cerebral CT or MR should be performed when the time from the stroke onset to the completion of femoral artery puncture of a patient is 6 (exclusive)-24h (inclusive), and his/her ASPECTS score should be ≥ 6. (If immediate CT perfusion imaging or MR perfusion imaging is feasible, it is recommended to perform CTP or MRP simultaneously to assist in the assessment of the infarct core, and his/her ASPECTS score should also be ≥ 6); 3) DSA angiography shows acute occlusion of large intracranial arteries, including intracranial internal carotid artery (C4-C7), middle cerebral artery (M1/M2), basilar artery and intracranial vertebral artery (V4).
General exclusion criteria	
 1) Those who could undergo neither MRI nor CT; 2) Those with hemorrhagic stroke or major ischemic stroke within 6 months before enrollment; 3) Those with severe persistent hypertension that could not be controlled by intravenous injection for blood pressure reduction, i.e. patients with sustained SBP > 185 mmHg or sustained DBP > 110 mmHg; 4) Those with presumed septic emboli or suspected bacterial endocarditis; 5) Renal failure, defined as creatinine > 3.0 mg/dL (264 μmol/L); 6) Those with blood glucose < 2.78 mmol/L (50 mg/dL) or > 22.20 mmol/L (400 mg/dL);

	
 7) Decreased platelet count ($< 40 \times 10^9/L$); 8) Those with known hemorrhage tendency, coagulation factor deficiency, are taking anticoagulants and with INR > 3.0; 9) Pregnant or lactating women; 10) Those with known severe allergy to contrast media or known allergy to nickel materials; 11) Those with disorders possessing possibility of affecting neurological assessment (e.g., neurological and psychiatric disorders); 12) Those who are unable to undergo interventional operations due to heart, lung, liver failure or other serious diseases; 13) Participating in clinical trials of other drugs or devices; 14) Life expectancy less than 6 months; 15) Other conditions judged by the investigator to be not suitable for inclusion.
Angiographic exclusion criteria	
 1) There is evidence of intracranial hemorrhage on CT or MR or known hemorrhage tendency; 2) CT/MR/DSA angiography suggests > 1 vascular occlusion (e.g., simultaneous occlusion of bilateral internal carotid artery vessels, or simultaneous occlusion of intracranial vessels in anterior and posterior circulation, or simultaneous occlusion of intracranial and extracranial internal carotid artery); 3) Those with carotid artery dissection, occlusion of the initial segment of the carotid artery or arteritis; 4) Those whose access vessels are severely tortuous, making the revascularization device difficult to reach the target location.
Primary endpoint	Success rate of instant recanalization
Secondary endpoints	Proportion of subjects with mRS scores of 0-2 on 90d postoperatively, time from femoral artery puncture to recanalization/the end time of operation for subjects whose recanalization failed, proportion of subjects with NIHSS score decrease > 4 , and success rate of device operation
Safety endpoints	Incidence of symptomatic intracranial hemorrhage within 24h postoperatively, all-cause mortality within 90d, incidence of SAE, incidence of AE, and incidence of device defects
Clinical examination items	
 ◆ Vital signs: heart rate, blood pressure ◆ Cerebral CT or MR ◆ Blood routine: Red blood cell, hemoglobin, white blood cell count, and platelet count ◆ Blood chemistry: Urea nitrogen (urea), serum creatinine, blood glucose ◆ Coagulation: Prothrombin time, activated partial thromboplastin time and INR ◆ Pregnancy testing (Only for women of childbearing potential who are planning to become pregnant) ◆ Cerebral vascular DSA
Expected duration of participation	Screening/baseline period (-1 d ~ 0 d preoperatively), treatment period (day of operation/0d), observation period (24 ± 12 h postoperatively), follow-up period (7 ± 2 d postoperatively (before discharge in case of premature discharge)), and follow-up period (90 ± 14 d postoperatively). The expected duration of participation of each subject is about 90 days.
Statistical analysis	Medical Statistics Office of Peking University First Hospital [name]
Contract research organization	JetMed (Beijing) Co., Ltd.
Expected	About 30 months

duration of trial	
-------------------	--

List of Abbreviations

Abbreviation	Terms and Definitions
AE	Adverse event
SAE	Serious adverse event
FAS	Full Analysis Set
PPS	Per Protocol Set
SS	Safety Analysis Set
eCRF	Electronic Case Report Form
AIS	Acute ischemic stroke
rt-PA	Recombinant tissue plasminogen activator
sICH	Symptomatic intracranial hemorrhage
SAH	Subarachnoid hemorrhage
NIHSS	National Institutes of Health Stroke Scale
TIMI	Thrombolysis in Myocardial Infarction
mTICI	Modified Thrombolysis in Cerebral Infarction
mRS	Modified Rankin Scale
ASPECTS	Alberta Stroke Program Early CT Score
INR	International Normalized Ratio
RHV	Rotating Hemostatic Valve

1. Sponsor Information

1.1. Name of Sponsor

Sponsor: Sinomed Neurovita Technology Inc.

1.4. Relevant Qualification Documents of Sponsor

Unified social credit code: 91320506MA2288DA27

1.5. Name, Address, Contact Information and Relevant Qualification Documents of Agent

N/A

2. List of Study Sites and Investigators

See Appendix 1 List of Study Sites and Investigators for details.

During the clinical study, if the existing participating sites fail to obtain the approval of the clinical trial administrative department or the Ethics Committee, resulting in the progress of the study significantly slower than the expected schedule, the sponsor should fully communicate and discuss with the coordinating investigator, and then make adjustments to the participating sites (abandonment or addition), and may update the list of clinical study sites in the Appendix without amending the text of the protocol. The final list of participating sites should be submitted to the clinical trial administrative department and Ethics Committee of all participating sites for filling.

3. Purpose and Content of Clinical Trial

3.1. Purpose

To verify that Ghunter Revascularization Device manufactured by Sinomed Neurovita Technology Inc. (hereinafter referred to as “Sinomed Neurovita”) is not inferior to Solitaire FR in success rate of instant recanalization for endovascular treatment of acute ischemic stroke, and to verify the effectiveness and safety of this product by clinical trial in accordance with the Good Clinical Practice for Medical Devices.

3.2. Contents

The study is a prospective, multicenter, randomized controlled, non-inferiority clinical trial, of which the investigational device is Sinomed Neurovita Ghunter Revascularization Device and the control device is Solitaire FR (hereinafter referred to as the control product under the trade name Solitaire FR) distributed by Covidien Healthcare International Trading (Shanghai) Co., Ltd.; the study is planned to be conducted in more than 10 sites and include 220 subjects. The subjects who meet the inclusion criteria will be randomized into the test group or control group in 1:1. The study is to collect and evaluate whether the success rate of instant recanalization is not inferior to Solitaire FR when Sinomed Neurovita Ghunter Revascularization Device is used for endovascular treatment of acute ischemic stroke, and to evaluate whether there is a statistically significant difference in the proportion of subjects with mRS score of 0 - 2 on 90d postoperatively, the time from femoral artery puncture to recanalization/the end time of operation for subjects whose recanalization failed, the proportion of subjects with NIHSS score decrease > 4 , and the success rate of device operation as compared with Solitaire FR when Ghunter Revascularization Device is used for endovascular treatment of acute ischemic stroke. Also, whether there is statistical difference in incidence of symptomatic intracranial hemorrhage within 24h postoperatively, all-cause mortality within 90d, incidence of SAE, incidence of AE, and incidence of device defects between Ghunter Revascularization Device and Solitaire FR for endovascular treatment of acute ischemic stroke will be evaluated.

4. Background of Clinical Trial

Stroke is one of the leading causes of disability and death in humans, and acute ischemic stroke (AIS) accounts for about 80% of all strokes. Recent studies have shown that the 1-month mortality rate of hospitalized acute ischemic stroke patients in China is 2.3%-3.2%; the 3-month mortality rate is 9%-9.6%, and the death/disability rate is 34.5%-37.1%; the 1-year mortality rate is 14.4%-15.4%, and the death/disability rate is 33.4%-33.8%^[1]. The key to AIS treatment lies in early recanalization of obstructed vessels and saving the ischemic penumbra. Current treatment modalities mainly focus on intravenous thrombolysis and endovascular treatment, of which endovascular treatment mainly includes arterial thrombolysis, non-stented mechanical thrombectomy, and stented mechanical thrombectomy^[2, 3].

At present, the proven effective treatment for early recanalization of AIS is intravenous recombinant tissue plasminogen activator (rt-PA) thrombolysis^[4-6]. A pooled analysis of 9 randomized controlled studies of thrombolysis published in 2014 further confirmed the benefit of intravenous rt-PA thrombolysis within 4/5h of ischemic stroke onset, and the earlier the time, the more the benefit^[7]. However, because intravenous thrombolysis has strict time window restrictions,

less than 3% of patients can benefit from it, and there is still a huge room for optimization of its therapeutic effect: compared with the control group, the mortality rate at 3-6 months after intravenous thrombolysis is not significantly reduced, still as high as 17.9%, and two-thirds of patients are still left with different degrees of disability, especially for patients with great vascular occlusion or severe disease, and its recanalization rate is low (13%~18%) [8].

Therefore, domestic and foreign scholars have been exploring the AIS endovascular treatment regime for patients with great vascular occlusion. Since September 2014, a series of studies have published more consistent findings: endovascular treatment based on mechanical thrombectomy can bring definite benefits [9-17].

Mechanical thrombectomy devices have gained much attention because of their many theoretical advantages: rapid recanalization, lower hemorrhage conversion rate, and prolonged stroke intervention time windows [15]. Merci Retrieval™ (2004) and Penumbra Stroke Systems™ (2008) were approved by the US Food and Drug Administration (FDA) as the first-generation mechanical thrombectomy devices.

The invention of stent thrombectomy devices represents a great advance for endovascular treatment of stroke, and revascularization devices have the advantage of navigability and rapid recanalization without the risk of long-term complications. The stent thrombectomy device uses a temporary stent to capture the thrombus and to restore flow by moving the thrombus against the intracranial vessel wall; upon stent withdrawal, the thrombus is captured in the stent space and removed with the stent. Solitaire (Medtronic/ev3) and Trevo (Stryker) stent thrombectomy devices were approved by the US FDA in 2012 for treatment of great-vessel occlusive stroke. The Solitaire device versus Merci device for AIS treatment trial (SWIFT) [18] compared the Solitaire and Merci devices (non-stented mechanical revascularization device) and terminated prematurely mid-term due to a significant difference in effectiveness; in the primary endpoint, recanalization was defined as a TIMI grade of 2 or 3. More recanalization with the Solitaire device, more patients with mRS scores ≤ 2 after 3 months. The multicenter randomized clinical trial of AIS endovascular treatment (MRCLEAN) [10] was a prospective, multicenter, randomized controlled study and was the first to exhibit a significant benefit of endovascular treatment compared with the standard internal medicine treatment; the results demonstrated a higher rate of 24h recanalization for endovascular treatment group, a smaller median infarct volume at 1 week, and a better 3-month mRS grade. The study, with endovascular mechanical thrombectomy as the primary endovascular treatment for AIS (SWIFT PRIME) [13] was conducted in 39 hospitals in the United States and Europe to compare the effectiveness of intravenous rt-PA thrombolysis with combined endovascular treatment (both using Solitaire), while it was terminated

prematurely as the interim analysis suggested a significant benefit of endovascular treatment; the results demonstrated that patients in the thrombectomy group had a higher proportion in mRS scores of 0-2 on 90d and a tendency to reduce mortality. In the EXTEND-IA ^[11], a prospective, randomized controlled study to prolong the time from acute neurological deficit to intra-arterial thrombolysis, subjects were randomized into the intravenous r-tPA thrombolysis group and intravenous r-tPA thrombolysis + Solitaire thrombectomy group; the results demonstrated that the early reperfusion rate of ischemic tissue at 24h after Solitaire thrombectomy, the early neurological improvement rate on 3d, and the proportion of patients with mRS scores of 0-2 on 90d in patients with thrombectomy were significantly higher than those in the control group, showing a tendency to reduce mortality. In summary, there is clear evidence to support the use of stent thrombectomy devices for early or ultra-early thrombectomy ^[2].

DEFUSE-3 ^[19] was a multicenter, randomized, open-label, blinded evaluation outcome (PROBE) clinical study to determine whether patients with great vascular (ICA or M1) occlusion within 6 - 16 h from the last time being normal could benefit from thrombectomy. The results demonstrated that the 90-d mRS score of mechanical thrombectomy + drug treatment group was significantly better than that of the drug treatment group, and the 90-d mortality was significantly reduced. The incidences of symptomatic intracranial hemorrhage and 24h vascular patency rate were similar to those of the drug treatment group. DEFUSE-3 focused more on mismatch between perfused ischemic area and core infarct. DAWN ^[20] was a study of thrombectomy taking a treatment time window of 6 - 24 h in patients with sleep stroke and out-of-time window stroke with clinical image mismatch, and its evaluation endpoints were similar to DEFUSE-3. In addition, 90-d mRS, 90-d mortality, 24-h infarct size increased, and symptomatic intracranial hemorrhage were also evaluated. The results demonstrated that the 90-d mRS was significantly improved in the thrombectomy group, and DAWN focused more on the mismatch between the patient's clinical symptoms and infarct size.

In the Chinese Guidelines for the Endovascular Treatment of Acute Ischemic Stroke (2018), mechanical thrombectomy for acute anterior circulation great-vessel occlusive stroke within 6h of onset is classified into Class I recommendation (Level A evidence). According to the results of DEFUSE-3 and DAWN studies, patients with onset at 6 - 16 h and 16 - 24 h met the corresponding inclusion and exclusion criteria and were classified into Class I recommendation (Level A evidence) and Class IIa recommendation (Level B evidence), respectively. According to the 2018 AHA/ASA ^[4], mechanical thrombectomy is recommended as Class I recommendation (Level A evidence) for acute ischemic stroke patients within 6-16h from the last time being normal and target lesions in

the anterior circulation great vessels if the enrollment meets the DOWM or DEFUSE-3 criteria. Mechanical thrombectomy is recommended as Class IIa recommendation (Level B evidence) in acute ischemic stroke patients within 6-24h from the last time being normal and target lesions in the anterior circulation great vessels if the enrollment meets the DOWM or DEFUSE-3 criteria.

At present, the self-expanding revascularization devices marketed in China include the ReVive SE (Self-Expanding) Thrombectomy Device (Trade Name: ReVive SE, NMPA (I) No. 2014 3773354), Solitaire FR Revascularization Device (Trade Name: Solitaire FR, NMPA (I) 2013 3774122) and Trevo ProVue (Trade Name: TrevoProVue, NMPA (I) 20153773927). Those products are all imported and are expensive. In view of this, on the premise of ensuring the safety and effectiveness, the localization and cost reduction of revascularization devices break the monopoly of foreign products, so that more stroke patients can receive advanced interventional therapy with mechanical thrombectomy, meeting the clinical and patient needs.

As independently developed by Sinomed Neurovita, Ghunter Revascularization Device has passed the test of Tianjin Medical Device Quality Supervision and Testing Center, NMPA (Test Report No.: 2021-GJ-0081). The safety and effectiveness of the product were further verified through animal experiment and therefore the conditions for conducting a clinical trial are met.

5. Characteristics, Device Composition, Working Principle, Mechanism of Action and Study Scope of the Product

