7.1.2. Statistical Analysis Methods

7.1.2.1. General Principles

Statistical description: The categorical data are described as frequency and proportion; while the continuous data are described as mean, standard deviation, maximum, minimum, median, 25th quantile, and 75th quantile.

Statistical inference: For the comparison of general situation of the two groups, the quantitative indicators between groups are compared using group t test or Wilcoxon rank sum test according to the data distribution, classification indicators using chi-square test or accurate probability method (if the chi-square test is not applicable), and ordinal data using Wilcoxon rank sum test or CMH test.

All statistical tests, if not specified, are two-sided and the difference is considered statistically significant when P value is <0.05 (two-sided). In addition to the statistical methods listed below, detailed and additional exploratory analyses may be required and confirmed in the Study Reports and Statistical Analysis Plan (SAP).

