7.1.2.5. Safety Indicator

The number and proportion of cases with normal conditions before treatment and abnormal conditions after treatment will be described respectively by the test group and the control group. AEs are described by the number and the incidence of AEs, where the likelihood ratio X^2 test or Fisher's exact probability test is used. Also, the manifestations and degree of AEs occurred in each group and their relationship to the investigational product will be described in detail.

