8.2. Pass/Fail Criteria for Clinical Trial Results

If the lower limit of the 95% CI of the difference in recanalization success rate between the test group and control group is greater than -12.5% (the pre-specified non-inferiority margin), and there are no clinically unacceptable safety issues related to the investigational device, the study is qualified, otherwise it is unqualified.

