1.3. Study Design

This is a prospective, multicenter, randomized controlled, non-inferiority clinical trial. The investigational device is the Intracranial Thrombectomy Stent (Sino Neurovita), with the comparator device being the Solitaire FR (Covidien Medical Device International Trading (Shanghai) Co., Ltd., hereinafter referred to by its trade name Solitaire FR). The trial is planned to be conducted at more than 10 clinical trial sites, enrolling 220 subjects. Eligible subjects were randomized 1:1 to either the study group or control group. The study evaluated whether the immediate recanalization rate of the Sinomed Neurovita Intracranial Thrombectomy Stent was non-inferior to that of the Solitaire FR when used for endovascular treatment of acute ischemic stroke. A central reading laboratory independent of the trial conducted blinded assessments of target vessel recanalization. The study evaluated whether there were statistically significant differences between the Sinomed Neurovita Intracranial Thrombectomy Stent and the Solitaire FR in the following outcomes for acute ischemic stroke endovascular therapy: 90-day mRS 0-2 rate, time from femoral artery puncture to recanalization or

procedure end time for non-recanalized subjects, proportion of subjects with NIHSS improvement ≥ 4 points, and device procedural success rate. Evaluate whether there are statistically significant differences between the Sinomed Neurovita Intracranial Thrombectomy Stent and Solitaire FR in the following outcomes for endovascular treatment of acute ischemic stroke: incidence of symptomatic intracranial hemorrhage within 24 hours post-procedure, all-cause mortality within 90 days, incidence of serious adverse events (SAE), incidence of adverse events (AE), and incidence of device failure.

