5.1. General Principles

Statistical analyses were performed using SAS version 9.4 statistical software.

Descriptive Statistics: Count data were described using frequency and proportion; continuous data were described using mean, standard deviation, maximum, minimum, median, and 25th and 75th percentiles.

Statistical Inference: For comparisons between two groups, quantitative indicators were analyzed using paired t-tests or Wilcoxon signed-rank tests based on data distribution. Categorical indicators were analyzed using chi-square tests or exact probability methods (if chi-square tests were not applicable). Ordinal data were analyzed using Wilcoxon signed-rank tests or the Cumulative

Hypothesis Test (CMH).

Unless otherwise specified, all statistical tests were two-tailed. A P-value < 0.05 (two-tailed) was considered statistically significant.

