5.5. Safety Analysis

The incidence of symptomatic intracranial hemorrhage within 24 hours postoperatively (data from the central reading center) and all-cause mortality within 90 days postoperatively were analyzed as categorical data.

Adverse events were described by the number of cases and incidence rate, with detailed descriptions of the specific manifestations, severity, and relationship to the study product for all adverse events that occurred.

The number and proportion of cases with normal findings before treatment and abnormal findings after treatment were described separately.

Device defects were described using incidence rates.

6. Statistical Analysis Results

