6.7.2. All-cause mortality within 90 days postoperatively

Table34 Study All-cause mortality within 90 days

Item	Indicator	Experimental Group	Control Group	Total
All-cause mortality within 90 days post-surgery	No n(%)			
	Yes n(%)			
	Total (Missing)			
	Statistic			
	P-value			

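### Safety against Solitaire FR is compared only by two-sided difference tests, with no risk difference or confidence interval planned to inform the safety half of the pass rule

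*Protocol*

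**What the plan says.** The purpose in protocol 3.1 covers the safety of the product as well as its effectiveness. Protocol 3.2 then poses the safety question as "whether there is statistical difference in incidence of symptomatic intracranial hemorrhage within 24h postoperatively, all-cause mortality within 90d", continuing with SAEs, AEs and device defects. SAP 1.3 uses the same form: "Evaluate whether there are statistically significant differences between the Sinomed Neurovita Intracranial Thrombectomy Stent and Solitaire FR in the following outcomes".

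The method follows from the general rules. SAP 5.1 states: "Categorical indicators were analyzed using chi-square tests or exact probability methods", two-sided at 0.05. SAP 5.5 says that haemorrhage within 24 hours and "all-cause mortality within 90 days postoperatively were analyzed as categorical data". For AEs, protocol 7.1.2.5 names a likelihood-ratio chi-square or Fisher's test.

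The table shells in SAP 6.7 match this. Tables 33 (haemorrhage), 34 (death) and 50 (device defects) hold n(%) by arm, a statistic and a P-value. Tables 36 to 38 hold numbers, incidence rates and a P-value. None has a column for the difference between arms or for its interval. A between-group interval is planned only for recanalization (protocol 7.1.2.3 and 8.2; SAP 5.4.1, Tables 24 and 27).

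Protocol 8.2 makes safety a second condition for passing. Besides the recanalization limit, it requires that "there are no clinically unacceptable safety issues related to the investigational device, the study is qualified, otherwise it is unqualified". No figure is attached to that condition. Protocol 7.2.1 sizes the trial on recanalization alone, and neither document states power for a safety endpoint.

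**The concern.** For effectiveness, the plan uses interval logic: an estimate, a confidence limit and a margin. For safety, it uses a test of no difference. In a trial of this size such a test says little when it is not significant, because a large excess of deaths or haemorrhages can easily give P > 0.05. The less information there is, the more likely that result becomes.

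The safety half of the pass rule is a clinical judgement. Those who make it need to know how large an excess risk the data still allow. The planned tables do not show this, so a non-significant P may be taken for reassurance that it cannot give.

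**Working it through.** **Step 1. Reproduce the plan's sample size.** Inputs from protocol 7.2.1: 89% in both arms, margin 12.5 points, one-sided 0.025, power 80%.

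n = (1.960 + 0.842)² × 2 × 0.89 × 0.11 / 0.125² = 98.4, so 99 per arm; 99 / 0.9 = 110. The stated 99 and 110 reproduce. No safety quantity enters.

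**Step 2. Inputs for the safety check.**
- Arm size: 110 as randomized, or 99 after the planned 10% dropout. SAP section 4 does not impute missing safety data.
- Control 90-day mortality: the documents give no rate for Solitaire FR. Protocol section 4 gives 9% to 9.6% at 3 months for hospitalized ischaemic stroke in China, and 17.9% at 3 to 6 months after intravenous thrombolysis. Both are used as a range.
- Control haemorrhage rate: none in the documents. A range of 3% to 8% is assumed.

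**Step 3. Chance of a non-significant result when a real excess exists.** For n per arm, control rate p_C and test rate p_T:

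miss = 1 − Σx Σy Bin(x; n, p_C) × Bin(y; n, p_T) × [P(x, y) < 0.05]

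P is from the Pearson chi-square test when all expected counts are at least 5, and otherwise from Fisher's test, two-sided. All outcomes are enumerated.

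| Endpoint | Control | Test | Missed, 110 per arm | Missed, 99 per arm |
|---|---|---|---|---|
| Death, doubling | 9% | 18% | 48.9% | 53.5% |
| Death, doubling | 9.6% | 19.2% | 46.0% | 50.6% |
| Death, doubling | 17.9% | 35.8% | 14.3% | 17.7% |
| Death, +10 points | 17.9% | 27.9% | 57.9% | 60.5% |
| Haemorrhage, doubling (assumed rate) | 3% | 6% | 85.7% | 88.4% |
| Haemorrhage, doubling (assumed rate) | 5% | 10% | 70.3% | 73.6% |
| Haemorrhage, doubling (assumed rate) | 8% | 16% | 54.1% | 58.3% |

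The choice of test matters somewhat. With Fisher's test throughout and 110 per arm, the doublings of death from 9%, 9.6% and 17.9% are missed 57.3%, 54.1% and 17.8% of the time. The likelihood-ratio test gives 48.9%, 46.0% and 13.8%.

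**Step 4. What an interval would add.** Suppose 10 of 110 control and 19 of 110 test subjects die. The difference is 17.3% − 9.1% = 8.2 points, and chi-square gives P = 0.07. The Wilson limits are 5.0% to 15.9% (control) and 11.3% to 25.4% (test). Newcombe limits for the difference:

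- lower: 0.0818 − √[(0.1727 − 0.1135)² + (0.1593 − 0.0909)²] = −0.9 points
- upper: 0.0818 + √[(0.2541 − 0.1727)² + (0.0909 − 0.0501)²] = +17.3 points

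Table 34 as planned would show the two rates and the P-value. It would not show that an excess of up to 17 points is compatible with the data. With 10 deaths in each arm, the same method gives −8.0 to +8.0 points.

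**The case against.** Four objections deserve weight.

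1. **The plan states no rule that non-significance means safety.** A reader might infer that it treats P > 0.05 as proof of equal safety, or that its inference is tilted towards the sponsor. The documents do not support this. They ask whether a difference exists, and protocol 8.2 rests on a clinical judgement about device-related issues with no P-value in it. This stands: the risk is of misreading, not of a faulty rule.

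2. **The P-value is not the only comparative evidence.** A reader might infer that it is. In fact Tables 33, 34, 36 to 38 and 50 show rates by arm. Tables 35 and 36 break events down by device-relatedness and fatal outcome, and Table 35 also by severity. SAP 5.5 asks for narrative description. A reader can derive a risk difference from the rates, and protocol 7.1.2.1 leaves room for further exploratory analyses. This also stands, so the claim is limited to planned inference.

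3. **The death figure depends on the control rate.** A reader might infer that a doubling of deaths is missed about half the time whatever the setting. That holds only near 9% to 9.6%, a rate for hospitalized stroke in general. The trial enrols patients with NIHSS of at least 6 and large-vessel occlusion. At 17.9% a doubling is missed about 14% of the time. The condition must be stated. It does not remove the point, because a doubling from 17.9% is an excess of 17.9 points, and a 10-point excess from that rate is still missed 58% of the time.

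4. **Without a margin, an interval leaves the pass rule a judgement.** True. The interval does not turn that judgement into a test; it supplies the size and uncertainty that the judgement needs.

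**Conclusion.** The concern holds as a gap in planned reporting. Safety is compared by difference tests alone, in a trial sized only for recanalization, and no interval for the excess risk is planned, although safety is a condition for passing.

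The size for 90-day death depends on the control rate. With 110 per arm, a doubling is missed 46% to 49% of the time at 9% to 9.6% (51% to 54% with 99 per arm), and about 14% at 17.9% (18% with 99). A 10-point excess over 17.9% is missed 58% of the time. For haemorrhage, a doubling is missed 86% to 54% of the time with 110 per arm, but only on an assumed control rate of 3% to 8%. These figures use a chi-square test with Fisher's test for small expected counts; Fisher's test throughout gives higher miss rates for death.

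The primary recanalization test is not affected.

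**What to change.** - In SAP 5.5 and Tables 33, 34 and 36, report the risk difference (test minus control) with a two-sided 95% confidence interval, by the Newcombe or Miettinen-Nurminen method, for symptomatic haemorrhage within 24 hours, 90-day death and subjects with any SAE.
- In protocol 3.2 and SAP 1.3, reword the question for these endpoints from whether a difference exists to estimating the difference with its 95% interval.
- In protocol 8.2 and the SAP, state that the safety judgement takes these estimates and intervals into account, and that P > 0.05 will not be reported as evidence of equal safety.

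The cost is wording and two columns in three tables. No new data, patients or safety margin are needed. The downside is that the report must show wide intervals, about ±8 points for death even with 10 events in each arm.
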